9.3 Other Efficacy Analyses

Efficacy analysis will be repeated on the subset of the PP dataset that was positive for allergic asthma at baseline. In addition, this subset will be assessed for differences in frequency of rescue inhaler use. Safety assessments may be repeated as exploratory using allergic asthma as a baseline co-variate. The use of immunologic response on end-of-study serum IgE testing may be used for exploratory correlative analysis of primary and secondary efficacy outcomes measured by the TCS. Additional predictors in the efficacy analysis multiple regression model will be assessed, including baseline allergen-specific serum IgE levels.

9.3.1 Laboratory Evaluations

To assess the induction of tolerance to the causative allergen using allergen-specific serum IgE testing changes (reduction) in mountain-cedar specific serum IgE reactivity will be assessed from pre-treatment to post-treatment (the end-of-study visit) as noted above in section 9.2. This is the only planned laboratory analysis.

10. SAFETY ANALYSIS

Safety analyses will compare treatment groups using appropriate methods according to their nominal or quantitative nature and will include descriptive statistics rather than formal hypothesis testing for noninferiority due to the small overall sample size. The study included a formal stopping rule in the event two systemic allergic reactions were detected.

The total safety score (TSS) and proportion of subjects with any treatment-emergent SAE, as defined in the composite safety endpoint, will be assessed using the Mann-Whitney test. Data will be presented in the form of descriptive statistics and appropriate tables and graphs with a conclusion on whether the significance level allowed the null hypothesis for each test to be rejected.

Safety Objective: To evaluate the safety profile of ILIT versus placebo using a standardized scoring system, the Total Safety Score worksheet, for AEs of interest (AEIs) up to 60 minutes post-procedure.

Statistical Analysis Plan

Safety Endpoints:

- Proportion of subjects experiencing a serious, treatment-emergent AE up to 60 minutes after an intranodal injection procedure
- Proportion of subjects experiencing systemic reactions to ILIT relative to placebo and severity of reactions relative to placebo as assessed by the Total Safety Score (TSS)
- Proportion of subjects reporting local injection site reactions relative to placebo and severity of local reactions relative to placebo, as assessed by the TSS

Additional safety tables and listings will include summaries of all patients experiencing anaphylaxis or treated with epinephrine, by group and a table of TSS reactions by severity by group.

Safety Population:

Safety analysis will include all participants who received at least one dose of study intervention regardless of whether they provided any diary data.

Calculation cumulative safety score (sum of TSS) across all patients by group will be performed in accordance with the scoring instruction described in section 7.4

10.2 Adverse Events

Spontaneously reported adverse events collected in the CRF will be summarized by counts and proportions according to body system classification and by group in tabular or narrative format.

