## 7 STUDY INTERVENTION DISCONTINUATION AND PARTICIPANT DISCONTINUATION/WITHDRAWAL

### 7.1 DISCONTINUATION OF STUDY INTERVENTION

Participants may choose to discontinue ILIT treatment at any time without prejudice. Discontinuing participation in the study will not preclude patients from continuing alternate allergy treatments. Patients may choose to continue as a patient of TASC or seek treatment elsewhere at their own expense. Discontinuation of ILIT treatment does not mean discontinuation from the study, and remaining study procedures should be completed as indicated by the study protocol to ensure patient follow-up through the end of the allergy season. Reasonable efforts will be made to contact the patient to encourage orderly completion of study discontinuation procedures. If a clinically significant finding is identified (including, but not limited to new medical conditions, adverse effects, or worsening of symptoms) after enrollment, the investigator or qualified designee will determine if any change in clinical patient management is needed. New clinically relevant finding will be reported as an adverse event (AE). For patients that discontinue the study prior to the scheduled end-of-study visit, the reason for discontinuation will be collected.

The data to be collected at the time of discontinuation will include the following:

- Adverse events, concomitant medications, reasons for discontinuation, vital signs

ILIT treatment of subjects may be discontinued at any time by the investigator any at any time the investigator determine that it is clinically a clinical determination that it is in the interest of the patient to discontinue treatment.

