## 8.2 SAFETY AND OTHER ASSESSMENTS

The following procedures will be performed as part of the safety and other assessment of the patient during this study:

- **Physical examination** including height and weight, body systems review
- **Vital signs** including temperature, pulse, respirations, and blood pressure
- **Special assays or procedures** include a Urine Pregnancy Test (UPT) for women of childbearing potential. As noted in Section 2, the risk of AIT during pregnancy is low, but immune sensitivity reactions and use of histamine in diagnostic allergy testing can be associated with pre-term delivery.

- **Administration of questionnaires** for patient-reported outcomes, including the NRS-11 for injection site pain, and treatment satisfaction.
- **Assessment of adverse events.** AEs/SAEs will be collected spontaneously and using the Total Safety Score (TSS) a structured worksheet for collecting and evaluating expected adverse events of interest (AEIs) associated with AIT.

In the event that a subject experiences either:

1. A treatment-emergent, serious adverse event that is related to study treatment, or
2. A grade 3 systemic allergic reaction according to WAO criteria, as assessed on the TSS worksheet that is possibly or definitely related to study treatment, or
3. Any other treatment-emergent adverse event resulting in death

The study will be placed on hold to further evaluate the risks and benefits of the study before a decision is made on whether or not to continue or terminate the study.

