## 8.3.4 TIME PERIOD AND FREQUENCY FOR EVENT ASSESSMENT AND FOLLOW-UP

The occurrence of an adverse event (AE) or serious adverse event (SAE) may come to the attention of study personnel during study visits and interviews, or other contacts with a study participant during the treatment and follow-up period.

All AEs will be captured on the appropriate case report form (CRF). Information to be collected includes event description, date of onset, clinician’s assessment of severity, relationship to study product as assessed by the investigator, and date of resolution/stabilization of the event. All AEs occurring while on study must be documented appropriately, according to the definitions in Section 8, regardless of

relationship. All AEs will be followed to adequate resolution or the end-of-the study. Local and systemic reactions during the 60-minute observation period will be captured on the Total Safety Score report form which includes specific criteria for assessing and grading adverse reactions to AIT. For patients experiencing a reaction, the observation period will be extended until the patient is stable. In accordance with Section 2.1, after each treatment visit, patients are counseled on how to recognize the signs of delayed-onset reactions, including worsening pain, tenderness, redness, swelling at the injection site and to assess the injection site for these symptoms for seven (7) following treatment. If they recognize these or other symptoms of a delayed-onset reaction, they are instructed to report these symptoms by phone.

Any medical condition that is present at the time that the participant is screened will be considered as baseline and not reported as an AE. However, if the study participant's pre-existing condition deteriorates at any time during the study, it will be recorded as an AE.

Changes in the severity of an AE will be documented to allow an assessment of the duration of the event at each level of severity to be performed. AEs characterized as intermittent require documentation of onset and duration of each episode.

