The investigator or designee will record all events, defined as serious, unexpected, and related adverse drug reactions with start dates occurring any time after the initiation of treatment until seven (7) days after the third treatment will be reported in accordance with the requirements of 21 CFR 312, if applicable, to the manufacturer using their post-marketing safety report system, and to the IRB as an Unanticipated Problem in accordance with Section 8.4. At each study visit, the investigator will inquire about the occurrence of AE/SAEs since the last visit. Unresolved adverse events will be followed for outcome information until the end of the study.

---

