10.5 Vital Signs

Vital signs were analyzed during the study as part of study monitoring using range checks and were reported as AEs in accordance with the criteria defined in the study protocol. Additional analysis of vital signs will not be performed.

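### The SAP does not flag serious adverse events that begin more than 60 minutes after injection, unless they are anaphylaxis or epinephrine-treated, and the scope of its general adverse-event summary rests on an undefined term

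*SAP*

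**What the plan says.** **General adverse events.** SAP 10.2 states: "Spontaneously reported adverse events collected in the CRF will be summarized by counts and proportions according to body system classification". Results are to be shown for each arm. The section makes no split by seriousness, severity or relationship, and because it allows a narrative in place of a table, a table is not guaranteed.

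**Serious events.** The SAP section 10 endpoint is "Proportion of subjects experiencing a serious, treatment-emergent AE up to 60 minutes after an intranodal injection procedure". The test named there for treatment-emergent serious events refers back to the composite safety endpoint. That composite, in protocol section 3 and SAP 2.1, also limits other serious events to 60 minutes after the procedure.

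**Other safety outputs.** SAP section 10 adds summaries of patients with anaphylaxis or given epinephrine, with no time limit stated, and a table of TSS reactions by severity and group. Protocol 9.4.8 plans individual-patient tables, restricted to serious events of interest.

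**Collection.** Protocol 8.2 says "AEs/SAEs will be collected spontaneously and using the Total Safety Score (TSS) a structured worksheet". Protocol 8.3.4 says "At each study visit, the investigator will inquire about the occurrence of AE/SAEs since the last visit" and requires every adverse event to be entered on the CRF. Under 8.3.3.1, worksheet events are not reported again as separate adverse events.

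**The concern.** There are two difficulties.

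The first is scope. In ordinary safety usage, a spontaneous report is one the patient volunteers. Much of this trial's ascertainment is by asking: protocol 8.3.4 requires it at each visit, and the checklists for the second and third injections and the end-of-study visit repeat it. The SAP does not say whether an event learned of in this way is inside or outside 10.2. Two analysts could produce different counts from the same database.

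The second is seriousness, and it does not depend on how the first is resolved. The protocol has seriousness, severity and relationship assessed, but 10.2 uses none of them, and the serious-event endpoint ends when the clinic observation hour ends. The protocol itself expects later reactions. Section 2.3.1 says systemic reactions can occur at any time after treatment, and 8.3.4 has patients counselled to watch for delayed reactions for seven days.

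What is at stake is the safety conclusion, which protocol 9.4.2 ranks ahead of efficacy. A reader of the planned outputs could not tell whether a late event in the body-system counts was serious.

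**Working it through.** No stated sample size, power or alpha is involved, so there is no plan figure to reproduce. The check is a reading of the passages against each other, with two short calculations.

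**1. Scope of 10.2**
- Literal reading: only volunteered events count. This conflicts with the visit inquiry and the all-event capture rule in protocol 8.3.4, and no other SAP output summarises non-worksheet events found by inquiry.
- Contextual reading: protocol 8.2 names two routes, spontaneous and worksheet. SAP section 10 follows the same division, with worksheet outputs first and 10.2 afterwards. On this reading 10.2 covers every CRF event not on the worksheet.
- SAP section 1 gives its own definitions priority for analysis, but supplies none for this term. The text leaves the choice open.

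**2. Where a serious event would be identified as serious, by type and timing**

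| Event | Output that would identify it |
|---|---|
| Any serious event within 60 minutes | Serious-event endpoint, SAP section 10 |
| Later anaphylaxis, or event treated with epinephrine | Anaphylaxis and epinephrine summaries, SAP section 10 |
| Later serious event of interest (allergic-reaction symptoms, protocol 8.3.8) | Individual-patient tables, protocol 9.4.8 |
| Any other later serious event | None; at most a body-system count in SAP 10.2 |

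The last row is the gap. It is the same under both readings in step 1. Under the literal reading, an event of that kind first learned of by asking might not be counted at all.

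**3. Time covered by the serious-event endpoint**
- Inputs: three injections; 60 minutes each (SAP section 10); an adverse-event period of each injection plus seven days (protocol 8.3.1).
- Endpoint windows: 3 × 1 h = 3 h.
- Adverse-event windows: 3 × 7 × 24 h = 504 h. They do not overlap: under the visit windows (Day 28 ± 3, Day 56 ± 6) the shortest gap between injections is (56 − 6) − (28 + 3) = 19 days, which exceeds 7.
- Share: 3 / 504 = 0.00595, about 0.6%.

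This is a share of time. It does not estimate the share of serious events missed, because protocol 2.3.1 says most severe systemic reactions begin within 30 minutes.

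**4. Weight of one patient**
With up to 16 patients per group (SAP 5.1), one patient is 1/16 = 6.25 percentage points of an arm, and more if the arm is smaller.

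**The case against.** The strongest defence is that protocol 8.2 uses the spontaneous route as its label for whatever is not on the TSS worksheet, and that SAP 10.2 inherits this. On that view, an event recorded on the CRF after a visit inquiry is already inside 10.2. This is a plausible reading, possibly the intended one. It removes any claim that elicited events are certainly omitted, but not the need to define the term.

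A reader might go further and infer that events found by inquiry, examination or vital-sign checks are left out of the only adverse-event table. The documents do not support that:
- 10.2 is not the only safety output. Section 10 also plans TSS, anaphylaxis and epinephrine outputs.
- Examination findings have a table (SAP 8.5) and a listing (SAP 10.6).
- SAP 10.5 says vital-sign findings "were reported as AEs in accordance with the criteria defined in the study protocol". That places them among the adverse events, though it does not settle whether they count as spontaneously reported.
- The documents give no split between volunteered and elicited events, so no undercount can be calculated.

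It can also be said that a serious late event would hardly pass unnoticed: protocol 8.2 places the study on hold after a treatment-related serious event or a treatment-emergent death, and 8.3.5 promises that adverse events will be analysed and published. This is fair, and it means one should not infer that the report would state no serious events when one had occurred. But a hold is a conduct measure and 8.3.5 specifies no table. Neither puts late serious events, by arm, into the planned analysis.

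**Conclusion.** The point holds in two parts of unequal strength.

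The firmer part is the serious-event gap. A serious event later than 60 minutes after injection that is not anaphylaxis, not treated with epinephrine and not an event of interest has no planned output that identifies it as serious. This is true whichever way 10.2 is read. Outside the 3 of 504 hours that the endpoint covers, identification depends on the event being one of those named types. The 504-hour figure assumes that all three injections are given and that protocol 8.3.1 sets the window. If the wider wording of 8.3.4 (all events while on study) governs, the covered share of time is smaller still.

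The weaker part is scope: the key term is undefined and its literal sense is too narrow, but the protocol offers a reading under which nothing is lost. This calls for clarification and does not show that events will be dropped.

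This is an inexpensive improvement to safety reporting. The documents do not show how many events it would affect, and it does not bear on the efficacy analysis.

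**What to change.** 1. In SAP 10.2, replace the opening words that limit the summary with: *All adverse events recorded in the CRF, however identified, other than those scored on the TSS worksheet*. Keep the body-system summary by group.
2. Add a table or listing, by arm, of all patients with any serious adverse event, with no 60-minute limit and including any serious event scored on the worksheet. Give onset relative to injection, severity and relationship. Protocol 8.3.4 already has onset date, severity and relationship recorded; onset can be given in hours only where a time was noted.
3. State the adverse-event window in the SAP. First reconcile protocol 8.3.1, which ties onset to each injection and the following seven days, with 8.3.4, which asks for all events while on study. The SAP wording should not settle this silently, because it would change what counts as an adverse event.

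The cost is one extra table or listing and a few words of SAP text, with no new data collection. The safety counts may look somewhat less favourable. The 60-minute endpoint can stay as it is. The change is best made before unblinding.

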10.5 Vital Signs

Vital signs were analyzed during the study as part of study monitoring using range checks and were reported as AEs in accordance with the criteria defined in the study protocol. Additional analysis of vital signs will not be performed.

10.6 Physical Examinations

Changes to physical examination finds from screening to end-of-study will be reported in a listing.
